17.1.10.5 Progressive Multifocal Leukoencephalopathy (PML)

Cases of PML have been reported in participants treated with acalabrutinib. Signs and symptoms of PML may include cognitive and behavioural changes, language disturbances, visual disturbances, sensory deficits, weakness, and coordination and gait difficulties.

If PML is suspected, hold further treatment with acalabrutinib until PML is excluded. A diagnostic evaluation may include (but is not limited to):

- Neurologic consultation
- Brain magnetic resonance imaging (MRI)
- PCR analysis for John Cunningham (JC) virus DNA in cerebrospinal fluid

If PML is confirmed, permanently discontinue acalabrutinib.

17.1.10.6 Haemorrhage

Bleeding events, some fatal, including CNS, respiratory, and gastrointestinal haemorrhage, have been reported in participants treated with acalabrutinib. Participants receiving antiplatelet or anticoagulant therapies may be at increased risk of haemorrhage and should be monitored for signs of bleeding. Should participants require either a vitamin K antagonist or combined administration of antiplatelet and therapeutic anticoagulation while on study, acalabrutinib treatment must be discontinued. As a precaution, it is suggested per protocol that acalabrutinib be withheld for at least 3 days pre- and post-surgery. Participants should be made aware of the risk of possible overlapping toxicities of haemorrhage while receiving both study treatments. Participants with haemorrhage should be managed per institutional guidelines or as clinically indicated. Coagulation should be monitored regularly as per the SoA. Avoidance of ibuprofen is advised.

17.1.10.7 Infections

Serious infections, including fatal events, have been reported in participants treated with acalabrutinib. Infection is an important potential risk for AZD4573 and an important identified risk for acalabrutinib. Participants should be made aware of the risk of possible serious infections while receiving combination study treatments. Investigators should be vigilant for signs of infection, especially opportunistic or fungal infections, and the possibility of hepatitis

B reactivation. Infections should be managed as per standard clinical practice. In case of Grade 3 infections, the guidelines provided in [Table 13](#) should be followed.

17.1.10.8 Cytopenia

Haematological toxicities including neutropenia, anaemia, and thrombocytopenia have occurred in participants treated with acalabrutinib. Neutropenia is an important identified risk for participants treated with AZD4573 or acalabrutinib. Cytopenia should be considered an overlapping toxicity for AZD4573 and acalabrutinib. In the presence of CTCAE Grade 3/4 neutropenia/leucopenia/thrombocytopenia/anaemia, participant's blood counts should be monitored, using local laboratories, at least every 48 hours until recovery.

In the clinical setting to date, Grade 3/Grade 4 neutropenia (~ 45% to 50%) has been observed in several participants with an onset around 24 hours after dosing AZD4573 monotherapy. Usually, neutrophils recovered spontaneously even without G-CSF.

Colony-stimulating factors including G-CSF, or pegylated G-CSF have been shown to work rapidly and may be used according to each Investigator site's institutional guidelines.

Anti-infective prophylaxis including anti-fungal prophylaxis should be used according to institutional guidelines. Antiviral or cotrimoxazole prophylaxis may not be used unless CD4 helper cell counts are less than 100 to 200 per microlitre.

Primary prophylaxis with G-CSF is not generally recommended. Anti-infective prophylaxis (antibiotics and antifungals) should be given in accordance with local hospital and International National Comprehensive Cancer Network (NCCN)/European Society for Medical Oncology (ESMO)/American Society of Clinical Oncology (ASCO) guidelines.

Please refer to [Table 13](#) for dose modifications due to haematological toxicities.

If the table indicates that the acalabrutinib dose should be reduced and the participant is already on 100 mg/day (see [Table 12](#)), acalabrutinib should be discontinued.

17.1.10.9 Liver Chemistry Test Abnormalities and the Risk of Liver Injury

Transaminase elevations are an important potential risk for patients treated with acalabrutinib, and an important identified risk for participants treated with AZD4573. Reactivation of hepatitis B infection has been observed in patients treated with acalabrutinib. Participants should be made aware of the risk of possible overlapping toxicities of transaminase elevations while receiving both drugs. Evidence of abnormal liver chemistry should be monitored as per the protocol guidelines. Increased levels of AST, ALT, or serum bilirubin should trigger an investigation of the cause, which may include viral infection or disease progression with liver infiltration. The Investigator should consider whether the abnormal liver chemistry meets the criteria for expedited reporting.

Bilirubin increase with transaminase increase is included as an important identified risk for AZD4573. Biochemical changes of increased transaminases with concomitant increase in bilirubin fulfilling criteria for Hy's law have been observed in participants treated with AZD4573. These events resolve rapidly and have to date not been associated with any adverse clinical sequelae or lasting liver damage. Upon rechallenge with AZD4573, there is no consistent pattern of recurrence, nor is there any consistent increase in severity of the events. As such, while the events follow the biochemical definition of Hy's law, the clinical pattern is rapidly self-limiting and does not seem to predict any lasting liver damage.

Participants who experience elevated ALT/AST $\geq 3 \times$ ULN and/or elevated total bilirubin $\geq 2 \times$ ULN after AZD4573 dosing must be closely monitored with repeated liver chemistry tests (INR, fibrinogen, D-dimer [where available at institution], ALP, ALT, AST, GLDH (if a GLDH test cannot be performed at the site or locally, LDH will be sufficient), CPK, total bilirubin, direct bilirubin, indirect bilirubin) are required at least every 48 hours (-2/+12 hours) after the start of the infusion and until resolution of the event. **CCI**

██████████ will also be collected (see Section [17.9.6](#)).

If bilirubin fails to resolve within 96 hours (-2/+12 hours) or transaminases fail to resolve within 7 days, or if the event is associated with significant clotting abnormality or clinical symptoms of liver disease, study treatment must be permanently discontinued (the participant remains on study for the 30-day SFU and long-term follow-up [LTFU] visits), and the event must be immediately communicated to AstraZeneca.

For guidance on treating liver toxicity, please refer to [Table 14](#) of this protocol.

During the course of the study the Investigator will remain vigilant for increases in liver biochemistry. The Investigator is responsible for determining whether a participant meets PHL criteria at any point during the study.

Please refer to [Appendix E](#) for the process to be followed to identify and appropriately report cases of PHL. It is not intended to be a comprehensive guide to the management of elevated liver biochemistries.

The Investigator will participate, together with the Medical Monitor, in review and assessment of PHL events to agree whether HL criteria are met. HL criteria are met if there is no alternative explanation for the elevations in liver biochemistry.

The Investigator is responsible for recording data pertaining to PHL/HL cases and for reporting AEs and SAEs according to the outcome of the review and assessment in line with standard safety reporting processes.

Regarding the hepatic toxicity events encountered to date with AZD4573, it has been observed that while the biochemical changes of increased transaminase with concomitant elevation in bilirubin seen in some participants could be classified as HL by its strict definition, they do not follow a pattern that is consistent with true HL predictive of hepatic injury, and are therefore 'PHL' cases. The events are rapidly resolved and to date have not led to any clinical sequelae or lasting hepatic injury. Repeated dosing with AZD4573 following these events has demonstrated that there is no consistent pattern of recurrence and no consistent increase in severity of the events if they do recur.

Available transcriptomic and clinical pathology data from the Phase I, FTIH study of AZD4573 monotherapy (D8230C00001) suggest the presence of an acute phase response in participants showing signs of liver injury. Thus, anti-inflammatory prophylaxis with steroids (eg, dexamethasone) could be expected to have a beneficial effect on incidence and severity of adverse effects on the liver related to AZD4573.

While, in the absence of a suitably-sized control group without prophylactic steroid administration, there is no confirmatory evidence for a positive effect of dexamethasone on liver safety profiles from available Phase I clinical data as yet, assessment of ALT changes from baseline versus cumulative dexamethasone dose suggests a possible trend towards a negative correlation, ie, higher dexamethasone doses being associated with smaller increases in ALT post-baseline.

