Event ^a	Action	
	AZD4573	Acalabrutinib
Isolated^b elevations in ALT, AST, or bilirubin		
Grade 1 Isolated ALT/AST \leq 3 \times ULN or Isolated Bilirubin \leq 1.5 \times ULN	Maintain current dose level. Monitor ALT, AST, ALP, and bilirubin at least 1x per week.	Maintain current dose level and schedule. Monitor ALT, AST, ALP, and bilirubin at least 1x per week.

Event ^a	Action	
	AZD4573	Acalabrutinib
Grade 2 Isolated ALT/AST > 3 to $\leq 5 \times$ ULN or Isolated Bilirubin > 1.5- $\leq 3 \times$ ULN	After 7 days if hepatic enzymes resolve to Grade ≤ 1 , rechallenge at same dose level.	Withhold or continue acalabrutinib (at Investigator discretion, after discussion with the Medical Monitor). To prevent disease progression, monitor disease parameters closely. Monitor ALT, AST, ALP, and bilirubin at least 1x per week. After 7 days if hepatic enzymes appear to be improving and acalabrutinib was withheld, restart acalabrutinib at current dose level.
Grade 3 Isolated ALT/AST > 5-20 \times ULN	If recovered to Grade ≤ 1 within 7 days, allow rechallenge at same dose level. If not recovered to baseline level within 7 days, discontinue AZD4573.	Withhold or continue acalabrutinib (at Investigator discretion, after discussion with the Medical Monitor). To prevent disease progression, monitor disease parameters closely.
Grade 3 Isolated Bilirubin > 3-10 \times ULN	If recovered to baseline level within 96 hours (-2/+12 hours) of the start of the infusion allow rechallenge at same dose level. If not, discontinue AZD4573	Monitor ALT, AST, ALP, and bilirubin at least 1x per week. After 7 days if hepatic enzymes appear to be improving and acalabrutinib was withheld, restart acalabrutinib with 1 level dose reduction or discontinue.
Grade 4^c Isolated ALT > 20 \times ULN or Isolated Bilirubin > 10 \times ULN	Discontinue AZD4573.	Discontinue acalabrutinib.
Grade 4 Isolated elevation ($\geq 20 \times$ ULN) in AST without concomitant elevation in ALT $\geq 20 \times$ ULN or concomitant elevation in TBL $\geq 2 \times$ ULN that fails to return to baseline level within 7 days from start of dosing	Discontinue AZD4573.	Discontinue acalabrutinib.

Event ^a	Action	
	AZD4573	Acalabrutinib

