Grade 4^c Isolated AST elevation $\geq 20 \times$ ULN without concomitant elevation in ALT $\geq 20 \times$ ULN or TBL $\geq 2 \times$ ULN	1st occurrence If recovered to Grade ≤ 1 or baseline level within 7 days of the start of the infusion allow rechallenge at same dose level 2nd occurrence If recovered to Grade ≤ 1 or baseline level within 7 days of the start of the infusion allow rechallenge with 1 dose level reduction 3rd occurrence Discontinue AZD4573	Withhold or continue acalabrutinib (at Investigator discretion, after discussion with the Medical Monitor). To prevent disease progression, monitor disease parameters closely. Monitor ALT, AST, ALP, and bilirubin at least 1x per week. After 7 days if hepatic enzymes appear to be improving and acalabrutinib was withheld, restart acalabrutinib at current dose level at the 1st occurrence and with 1 level dose reduction at the 2nd occurrence . Discontinue acalabrutinib at the 3rd occurrence .
Concurrent elevations in ALT, AST, or bilirubin (Please also refer to Appendix E for actions to be taken in the event of PHL)		
ALT or AST $\geq 3 \times$ ULN with TBL $\geq 2 \times$ ULN (Potential Hy's Law) AND INR $\geq 1.5 \times$ ULN (or $\geq 1.5 \times$ baseline if elevated at baseline) of any duration	Discontinue AZD4573.	Discontinue acalabrutinib.
ALT or AST $\geq 3 \times$ ULN with the appearance of fatigue, nausea, vomiting, right upper quadrant pain or tenderness, fever, rash, and/or eosinophilia $> 5\%$	Discontinue AZD4573.	Discontinue acalabrutinib.
ALT or AST $\geq 3 \times$ ULN and TBL $\geq 2 \times$ ULN where TBL does not return to baseline level within 96 hours (-2/+12 hours) from start of dose and/or AST or ALT do not return to baseline level within 7 days from start of dose	Discontinue AZD4573.	Discontinue acalabrutinib.

Event ^a	Action	
	AZD4573	Acalabrutinib
Grade 3 elevation ($\geq 5 \times$ ULN) in ALT or AST with TBL elevation above baseline level or ULN, but $< 2 \times$ ULN that do not return to baseline level within 7 days	Discontinue AZD4573.	Discontinue acalabrutinib.

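### Section 17.1.10.9 and Table 14 give opposing instructions for isolated Grade 2 liver chemistry rises: permanent stop versus rechallenge or continue

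*Protocol*

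**What the plan says.** **Section 17.1.10.9.** Close monitoring applies after ALT/AST of at least 3 x ULN, joined to bilirubin of at least 2 x ULN by "ULN and/or elevated total bilirubin", so isolated rises are included. The next paragraph sets the stop: "If bilirubin fails to resolve within 96 hours (-2/+12 hours) or transaminases fail to resolve within 7 days", or if there is significant clotting abnormality or clinical symptoms, then "study treatment must be permanently discontinued (the participant remains on study" for the 30-day and long-term follow-up visits. The sponsor is told at once. The following sentence refers to Table 14 for guidance.

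**Table 14, isolated Grade 2 row** (ALT/AST above 3 and up to 5 x ULN, or bilirubin above 1.5 and up to 3 x ULN).
- AZD4573: "After 7 days if hepatic enzymes resolve to Grade" 1 or lower, rechallenge at the same dose.
- Acalabrutinib: withhold or continue, at the Investigator's discretion after discussion with the Medical Monitor; then "After 7 days if hepatic enzymes appear to be improving and acalabrutinib was withheld, restart acalabrutinib at current dose level".

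**Table 14, isolated Grade 3 rows.** For bilirubin and AZD4573: "If recovered to baseline level within 96 hours (-2/+12 hours) of the start of the infusion allow rechallenge at same dose level", otherwise discontinue. For acalabrutinib: "After 7 days if hepatic enzymes appear to be improving and acalabrutinib was withheld, restart acalabrutinib with 1 level dose reduction or discontinue".

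**Table 14, concurrent rises.** Both drugs are discontinued in the row worded "where TBL does not return to baseline level within 96 hours (-2/+12 hours) from start of dose and/or AST or ALT do not return"; the ALT/AST limit in that row is baseline by day 7.

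**The concern.** The stop in 17.1.10.9 is mandatory and permanent, and it follows directly on a trigger that admits isolated rises. Table 14 keeps the same participant on treatment if the rise is isolated and Grade 2. A site that follows 17.1.10.9 ends treatment in a population with no standard therapy available (Section 14.1). A site that follows Table 14 re-doses someone whom 17.1.10.9 says must stop. Transaminase increase, and bilirubin increase with transaminase increase, are important identified risks of AZD4573 (Section 2.3.1); isolated bilirubin increase is not itself listed there.

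The rest of the protocol does not settle which text prevails. The retreatment criteria (Section 15.12.1) test hepatic recovery against Table 14's timeframes. The introduction to Section 17.1.10 says that Grade 1 and 2 toxicities generally need no dose reduction and points to Tables 13 and 14 for Grades 3 and 4.

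**Working it through.** There is no plan figure to reproduce. The check sets the two rules side by side.

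**1. Overlap.** 17.1.10.9 starts at ALT/AST 3 x ULN or bilirubin 2 x ULN. The Grade 2 row spans ALT/AST above 3 to 5, or bilirubin above 1.5 to 3. Both therefore apply to isolated ALT/AST above 3 to 5 x ULN and to isolated bilirubin of 2 to 3 x ULN.

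**2. Clocks.** The bilirubin window in 17.1.10.9 closes at 96 + 12 = 108 h. Table 14 decides on AZD4573 after 7 x 24 = 168 h and sets no upper limit.

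**3. Rises unresolved at the 17.1.10.9 limit** (96 h for bilirubin, 7 days for ALT/AST), where 17.1.10.9 always says stop:

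| Isolated rise | Table 14: AZD4573 | Table 14: acalabrutinib |
|---|---|---|
| Grade 2 ALT/AST | no action given | continue, or restart at current dose if improving |
| Grade 2 bilirubin, 2 to 3 x ULN | same dose once Grade 1 or lower after 7 days | continue, or restart at current dose if improving |
| Grade 3 ALT/AST | discontinue | if improving, reduce or discontinue |
| Grade 3 bilirubin | discontinue | if improving, reduce or discontinue |
| Grade 4 ALT or bilirubin; Grade 4 AST not back to baseline in 7 days | discontinue | discontinue |

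The Grade 3 acalabrutinib text is split over two rows in the extracted table and is taken here as one merged cell.

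**4. Two illustrative courses** (values assumed).
- No Gilbert's syndrome, so entry bilirubin was at most 1.5 x ULN (Table 2). Isolated bilirubin is 2.5 x ULN at 24 h, 2.2 at 96 h and 1.2 after 7 days. Since 2.2 > 1.5, it is unresolved at 96 h whether the test is baseline, Grade 1 or the entry limit. 17.1.10.9 stops treatment permanently. Table 14 gives AZD4573 at the same dose and keeps acalabrutinib at 100 mg twice daily.
- Isolated ALT is 4 x ULN, falling to 3.2 at day 7. This is above the Grade 1 limit (3) and the entry limit (below 3.0). 17.1.10.9 gives acalabrutinib 0 mg/day; Table 14 gives 2 x 100 = 200 mg/day. Table 14 is silent on AZD4573.

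**5. Dependence on readings.**
- If hepatic enzymes in the Grade 2 row exclude bilirubin, that row gives no AZD4573 action for bilirubin and 17.1.10.9 fills the gap. The acalabrutinib conflict for ALT/AST remains.
- If study treatment means AZD4573 alone, only the AZD4573 bilirubin conflict remains.
- If both readings fail, there is no conflict.

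The both-drugs reading is well supported. Section 13.1 glosses study treatment that way, and 17.1.10.9 sends the participant to follow-up visits that Sections 17.1.9.1 and 17.1.9.2 start when both drugs have stopped.

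**6. Recovery criterion.** 17.1.10.9 does not define resolution. Table 14's concurrent discontinue row uses baseline; its last concurrent row uses Grade 1 or lower, or baseline.

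**The case against.** The best defence is that 17.1.10.9 was meant for concurrent rises only. Its four elements (bilirubin at 96 h, transaminases at 7 days, clotting, symptoms) mirror Table 14's concurrent discontinue rows, and much of the surrounding text concerns potential Hy's Law. On that view the and/or threshold governs monitoring alone, and there is no conflict. This is plausible, but the text does not say so. Where the protocol means concurrent rises it states them, as in Section 15.2, the Hy's Law group of DLTs in Section 15.3, and Table 14's concurrent rows.

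A second defence is that Table 14 is headed as recommended, its Grade 2 acalabrutinib cell is discretionary, and a site can simply obey the mandatory text. That would be the cautious default. It still leaves a Grade 2 cell with no discontinue option and a retreatment test tied to Table 14, both at odds with the stop.

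A third is that the site does not decide alone. The Medical Monitor is contacted if an event is unresolved at 96 h (Section 17.1.6) and discusses Grade 2 acalabrutinib decisions. That stands as mitigation, but the visible text gives the monitor no rule of precedence.

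A reader might go further and infer that Table 14 conflicts with 17.1.10.9 throughout, or count the conflicting cells. The documents do not support this. AZD4573 agrees in the Grade 3 rows, Grade 3 acalabrutinib is looser but compatible because it permits discontinuation, and Grade 4 agrees. Any count would also split a single printed Grade 2 row and depend on both readings above.

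**Conclusion.** The concern holds for isolated Grade 2 rises only. As written, 17.1.10.9 stops treatment permanently where Table 14 re-doses AZD4573 (bilirubin of 2 to 3 x ULN that settles late, if hepatic enzymes include bilirubin) or keeps acalabrutinib (values improving but unresolved, if study treatment means both drugs). No visible text resolves it; Appendix E, to which Table 14 refers for potential Hy's Law, is not in the text at hand.

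The number affected is unknown and likely small. Recruitment has stopped (Section 4.1), and an isolated bilirubin rise requires ALT and AST below Grade 1. Reach is not nil: Section 6.13 lets participants continue after data cut-off under this protocol and the IB, although Section 15.7 points to the current IB. DLTs are defined separately, so no effect on dose escalation or on an endpoint is shown.

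A reader might also infer that the 17.1.10.9 rule is simply too strict and need only be narrowed. The documents do not show which rule the sponsor intends. Narrowing it alone would remove the only explicit AZD4573 stop for isolated Grade 2 ALT/AST unresolved at day 7. The correction should be made, with medium confidence, because two safety instructions disagree and aligning them is easy.

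**What to change.** Make the two texts agree, in one of two ways.

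**(a) If the stop is meant for concurrent rises.**
- Limit the 96-hour/7-day clause of 17.1.10.9 to ALT/AST of at least 3 x ULN together with bilirubin of at least 2 x ULN, the scope used in Sections 15.2 and 15.3 and in Table 14's concurrent discontinue row.
- Leave the clotting and symptom clauses unchanged.
- Name AZD4573 and acalabrutinib in place of study treatment.
- State that isolated rises follow Table 14.
- In the same change, add to Table 14's isolated Grade 2 AZD4573 cell an action for ALT/AST or bilirubin not at Grade 1 or lower by day 7: do not re-dose, and discontinue AZD4573, in line with the Grade 3 ALT/AST row. No stop is then lost.

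**(b) If the stricter rule is intended.** Add the 96-hour bilirubin stop and the 7-day ALT/AST stop, for both drugs, to Table 14's isolated Grade 2 and Grade 3 rows.

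In either case use one recovery criterion in 17.1.10.9 and in Table 14's concurrent discontinue and rechallenge rows.

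The cost is a few sentences in an amendment or site clarification letter; no new data or participants are needed.

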17.1.10.10 Tumour Lysis Syndrome (TLS)

Tumour lysis syndrome is an important identified risk for AZD4573 and an identified risk for acalabrutinib. **TLS prophylaxis is mandatory for all participants** starting 3 days before the first dose of AZD4573, which should be followed in addition to institutional guidelines.

Tumour lysis syndrome is characterised by the rapid and/or massive release of intracellular constituents (potassium, phosphorus and nucleic acids that can be metabolised to uric acid) following tumour cell lysis, resulting in life-threatening complications including acute kidney injury, arrhythmias, and neurological complications. While TLS can be seen in solid tumours, it is most prevalent in haematological malignancies, particularly bulky, chemosensitive diseases such as AML. Prevention and management of TLS is dependent on risk stratification, and risk-based prophylaxis and management (Howard et al 2011). Participants identified with TLS potential per published risk guidelines (Coiffier et al 2008; Table 16) should be provided with adequate hydration, pharmacological pre-treatment with allopurinol or rasburicase, and be carefully monitored for development of TLS.

Instructions for TLS prophylaxis are presented in Section 17.1.10.10.1, instructions for management of hydration are presented in Section 17.1.10.10.2, and instructions for

monitoring and maintenance of TLS are presented in Section [17.1.10.10.3](#). The Howard modification of Cairo-Bishop criteria for clinical and laboratory TLS are included in [Appendix F](#).

Laboratory or clinical TLS (please refer to [Appendix F](#) for definitions) may trigger dose modification in accordance with guidelines provided in [Table 13](#).

